## Section 5: Trial Population

Section/Item	Index	Description
Screening data	21	The number of PCIs performed, participants screened, and reasons for screening failure were collected by each study site. These data were reviewed by study staff to monitor recruitment and enrollment progress throughout the study.
Eligibility	22	
Inclusion Criteria
 
 
1. Male and female subjects, <math>\geq 18</math> to <math>\leq 80</math> years at time of study
 
2. Status post PCI with stent implantation requiring antiplatelet therapy
 
3. Willingness to comply with all study-related procedures
 
 
Exclusion criteria:
 
 
1. Pending imminent surgery placing patients at increased risk for bleeding with prasugrel or ticagrelor.
 
2. History of intracranial hemorrhage, TIA, and stroke
 
3. Active bleeding
 
4. Need for long-term anticoagulation (i.e. warfarin, dabigatran, rivaroxaban, apixaban, edoxaban, or lovenox).
 
5. Current or prior (within the past four weeks) treatment with voraxapar (Zontivity).
 
6. Severe renal or hepatic impairment
 
7. Treating physician does not want subject to participate
 

Recruitment	23	The number of participants assessed for eligibility along with reasons for non-enrollment will be reported as available.
Withdrawal/ follow-up	24a	The numbers of withdrawal from follow-up clinical assessments were reported as the intervention is a one-time event.
	24b	The number and time post randomization of voluntary withdrawals by participants or lost to follow-up were reported.
	24c	Reasons for voluntary withdrawal or lost to follow-up were reported if available.
Baseline patient characteristics	25a	Sex, race, age, hospital site, presence of acute coronary syndrome (ACS), insurance type, work status, tobacco use, past medical history, medications prior to admission.
	25b	For categorical variables, frequencies and percentages were reported. For continuous variables, the number of subjects, mean and standard deviation were reported by randomization group.

## Section 6: Analysis

Section/Item	Index	Description
Outcome definitions	26a	
Primary outcome: The number and proportion of participants receiving prasugrel/ticagrelor at discharge from index PCI in each randomized. Timing <7 days
 
Secondary Outcomes:
 
 
1. Adherence to the CPIC guideline suggested antiplatelet therapy recommendations based on genotype (intervention group only). Timing <7 days.
 
2. Major adverse cardiac events (MACE) defined as cardiovascular death, myocardial infarction, stroke, urgent need for revascularization, and stent thrombosis (Academic Research Consortium “definite” stent thrombosis). Timing at last follow-up.
 
3. Major bleeding events as defined by the Bleeding Academic Research Consortium (BARC) type 3 or 5. Timing at last follow-up.
 
4. Non-cardiac mortality. Timing at last follow-up.
 
5. Implementation Metrics. Timing < 7days 
 
a. Genotype test turnaround time (Time result reported to physician – time of buccal swab).
 
b. Number of inconclusive results.
 
 
 

	26b	n/a
	26c	Time to MACE or major bleed
Analysis methods	27a	
Primary outcome: Discharge antiplatelet therapy choice by genotyped and usual care group was compared using the chi-square or Fisher's exact test. The probability of receipt of antiplatelet agents was determined by logistic regression.
 
Secondary outcomes:
 
 
1. The adherence rate to the genotype guided recommendations for the genotyped group was determined by reporting the number of participants with LOF variants that received prasugrel or ticagrelor + the number of participants without these variants that received clopidogrel divided by the total number in the genotyped arm.
 
2. Clinical outcomes. Frequencies of CV related death, MI, stroke urgent, need for revascularization and stent thrombosis was reported as well frequencies of bleeding complications and compared using chi-square test or Fisher's exact test when appropriate. The time to first major cardiac event as a composite endpoint (CV related death, MI, stroke urgent need for revascularization and stent thrombosis) was determined. The incidence of first MACE and first major bleeding events between the groups was compared by use of Kaplan-Meier estimators and statistical tests evaluated based on log-rank tests.
 
3. Implementation. The turnaround time for test result in the
 

		genotyped group was presented as mean ± standard deviation (hours).
27b	n/a	
27c	n/a	
27d	n/a	
27e	n/a	
27f		To evaluate whether genotyping influenced MACE outcomes in participants with ACS, an interaction term between ACS and group assignment was tested in a Cox proportional hazard model.
Missing data	28	For time to MACE analysis, participants were censored at the date of event or time of known last follow-up.
Additional analyses	29	Post-hoc analyses Genotype was determined in the control group at the end of the trial. We combined the groups and evaluated outcomes by CYP2C19 genotype and antiplatelet drugs prescribed at discharge. Participants were grouped into the following categories: 1) Carriers of normal function alleles receiving any antiplatelet drug, 2) LOF carriers receiving clopidogrel, or 3) LOF carriers receiving prasugrel or ticagrelor. Time to MACE, major bleeding and a composite safety/efficacy endpoint consisting of MACE, major bleeding and non-cardiac mortality was determined in the three groups. Cox proportional hazards models were used to assess the effects of having an LOF allele and receiving clopidogrel therapy, having an LOF allele and receiving alternative therapy, and not having an LOF allele on the occurrence of first MACE, first major bleed, and first composite outcome. The Cox model was controlled for age at entry to the study, the date of catheterization, gender, race, hospital site, and history of ACS, smoking, hypertension, diabetes, and myocardial infarction.
Harms	30	No harms as a result of the genotyping intervention were reported.
Statistical software	31	Stata's V13.1 (College Lake, TX)
References	32	
1.Mega, J.L. et al. Reduced-function CYP2C19 genotype and risk of adverse clinical outcomes among patients treated with clopidogrel predominantly for PCI: a meta-analysis. JAMA 304, 1821-30 (2010).
 
2.Scott, S.A. et al. Clinical Pharmacogenetics Implementation Consortium Guidelines for CYP2C19 Genotype and Clopidogrel Therapy: 2013 Update. Clin Pharmacol Ther 94, 317-23 (2013).
 
 
4.Mehran, R. et al. Standardized Bleeding Definitions for Cardiovascular Clinical Trials: A Consensus Report From the Bleeding Academic Research Consortium. Circulation 123, 2736-47 (2011).

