### **6.7 Collection of saliva for future genetic tests**

An optional component of the study will be saliva collection for DNA biobanking. If the subject provides consent for this component, a saliva sample will be collected with the Oragene-DNA 500 kit (DNA Genotek. This is the same sample we are collecting in 6.2 above for the control group and not a separate sample. To avoid confusion for subjects and study personnel, a saliva sample will be collected for all participants and the purpose will be labeled (e.g. for *CYP2C19* genotyping only OR for biobanking and *CYP2C19* genotyping).

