### 7.1 Primary endpoints

1. We will tabulate the number and proportion of prasugrel/ticagrelor in each Arm. We will compare discharge antiplatelet therapy choice between the genotype and control arm using the chi-square or Fisher's exact test. The probability of receipt of antiplatelet agents will be determined by logistic regression.

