### Section 3: Study Methods

Section/Item	Index	Description
Trial Design	9	This was a prospective, pragmatic, randomized, controlled clinical pharmacogenetic implementation trial. Patients undergoing PCI with stent implantation requiring anti-platelet therapy were randomized 1:1 to either rapid genotyping of CYP2C19 with reporting of results to the interventional cardiologist or no genotyping (usual care).
Randomization	10	We used Stata's V13.1 (College Lake, TX) random number generator to draw random numbers that were used to randomize participants to the genotyping and usual care groups. Randomization was stratified by hospital site and by the presence or absence of ACS. Acute coronary syndrome was defined as unstable angina, non-ST elevation myocardial infarction, or ST-elevation myocardial infarction. The designation of ACS vs. stable angina was made by the treating interventional cardiologist. Within each of the four groups, randomization was balanced so that after every 10 patients, 5 were randomized to the genotyped group and 5 to usual care.
Sample size	11	The sample size calculation was based on two factors: 1) the rate of pre-study prasugrel/ticagrelor use (20%) and 2) anticipated increase in prasugrel/ticagrelor prescribing based on the frequency CYP2C19 LOF variants (~30-35%). We estimated a 15% difference in the use of prasugrel/ticagrelor in the two groups (35% in the genotyped group and 20% in the control group). A sample size of 138 per group (a total of 276) would provide 80% power at an alpha level of 0.05 to detect this difference. We increased our sample size to ~250 per group to allow for subgroup comparisons (e.g. ACS vs. stable coronary disease).
Framework	12	Genotyping will increase the prescribing of prasugrel or ticagrelor from the baseline rate of 20%.
Statistical interim analyses and stopping guidance	13	No interim analyses planned.
Timing of final analysis	14	Participants were followed until May 31, 2017 for prospective clinical endpoints assessment with the intention of a 12 month follow-up time for each participant. All analyses were performed collectively after May 31, 2017.

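### The crude primary comparison is valid but leaves precision unused by not standardising over CYP2C19 loss-of-function status, which is to be obtained in both arms

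*SAP*

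**What the plan says.** The primary outcome in SAP Section 6 (item 26a) is "The number and proportion of participants receiving prasugrel/ticagrelor at discharge from index PCI in each randomized" arm. Item 27a gives the analysis: "Discharge antiplatelet therapy choice by genotyped and usual care group was compared using the chi-square or" Fisher's exact test. It adds a model: "The probability of receipt of antiplatelet agents was determined by logistic regression". Protocol 7.1 plans the same: "The probability of receipt of antiplatelet agents will be determined by logistic regression". Neither document names a covariate for that model.

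Genotype is used elsewhere: in the adherence rate, which concerns the genotyped arm only, and in the post-hoc Cox models for clinical outcomes. It is not a randomisation stratum (SAP item 10 lists hospital site and ACS), nor is it among the baseline characteristics in item 25a.

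Genotype is nevertheless planned for everyone. Arm 1 is typed by buccal swab on the rapid device, and Arm 2 from saliva on an array (Protocol 6.2). SAP item 29 says "Genotype was determined in the control group at the end of the trial", and Protocol 6.7 says "a saliva sample will be collected for all participants".

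**The concern.** The intervention works by tying the drug to LOF status: carriers are recommended prasugrel or ticagrelor, and non-carriers clopidogrel. The Arm 1 rate therefore moves with the share of carriers who happen to be allocated there, and nothing in the design balances that share. A crude comparison carries this chance variation into the primary difference.

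LOF status is fixed before randomisation and allocation cannot change it, so measuring it late in controls does not disqualify it as a baseline covariate. At stake is the width of the primary confidence interval, and power if the true difference is smaller than planned or is estimated within subgroups.

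**Working it through.** **Inputs from the documents.** Expected use is "35% in the genotyped group and 20% in the control group" (SAP item 11). LOF carrier frequency is about 30-35% and the planned size about 250 per group (Protocol 7.5, SAP item 11). Allocation is 1:1 (SAP item 9).

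**Inputs assumed.** Adherence, because no expected rate is given. Control use is taken as 20% in carriers and non-carriers alike, because control prescribers do not see the genotype.

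**1. The plan's own figure.** Two-sided, pooled, no continuity correction:

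n = [1.96·√(2·0.275·0.725) + 0.84·√(0.35·0.65 + 0.20·0.80)]² / 0.15² = 137.9, so 138 per group, as stated.

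**2. Formulas.** Let q be the carrier share, pc and pn the Arm 1 use in carriers and non-carriers, p1 = q·pc + (1−q)·pn, and p0 = 0.20.

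- Crude: n·Var = p1(1−p1) + p0(1−p0).
- Standardising to the pooled LOF distribution removes q(1−q)(pc−pn)²/2. The factor ½ arises because the pooled carrier share rests on twice as many people and still varies.

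**3. Ceiling (q = 0.35, pc = 1, pn = 0).** Crude n·Var = 0.2275 + 0.1600 = 0.3875. Removed: 0.2275/2 = 0.11375. Left: 0.27375. The cut is 0.11375/0.3875 = 29.4%. At 250 per arm the standard error (SE) falls from √(0.3875/250) = 3.94 points to √(0.27375/250) = 3.31 points. A simulation of 100,000 trials gave a cut of 29.0% and a mean difference of 0.150 for both estimators. With genotype unrelated to prescribing, the simulated change was −0.2%, meaning no gain.

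**4. Partial adherence (q = 0.35, 250 per arm).** Adherence is q·pc + (1−q)(1−pn), the SAP item 19b definition. Power is Φ(difference/SE − 1.96).

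| Use in carriers / non-carriers | Adherence | Difference (points) | Variance cut | SE cut | Power, crude → standardised |
|---|---|---|---|---|---|
| 100% / 0% | 100% | 15.0 | 29% | 16% | 96.8% → 99.5% |
| 80% / 10% | 86.5% | 14.5 | 14% | 7.5% | 95.8% → 97.9% |
| 70% / 15% | 80% | 14.25 | 9% | 4.6% | 95.3% → 96.7% |
| 60% / 15% | 76% | 10.75 | 6% | 3.1% | 79.5% → 82.0% |

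**5. Carriers at 30%, the lower end of the plan's range.** Full adherence gives 30% versus 20%, a difference of 10 points rather than 15. Power at 250 per arm rises from 74% to 87%. With 80%/10% use (11 points) it rises from 81% to 87%, with 70%/15% (11.5 points) from 84% to 87%, and with 60%/15% (8.5 points) from 61% to 63%.

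**6. Within an ACS stratum.** Assume an even split, so 125 per arm, and 35% carriers. Power for the arm difference inside one stratum rises from 77% to 89% at full adherence, and from 74% to 81% with 80%/10% use. This is not the power of an ACS interaction test.

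**The case against.** The strongest reply is that no error has been shown. The chi-square or Fisher comparison is valid under randomisation, its estimate is unbiased, and covariate adjustment is the analyst's choice. That stands: the point concerns efficiency only.

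A reader might go further in four ways that the documents do not support.

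- *That 29% is the expected saving.* It requires every Arm 1 carrier and no non-carrier to receive prasugrel or ticagrelor. The protocol leaves the choice to the physician, limits the alternatives to patients without contraindications, and treats physician uptake as unknown.
- *That the trial is underpowered without adjustment.* At 35% versus 20%, power is already about 97%. The 74% to 87% gain belongs to a 10-point difference.
- *That carrier share is the largest removable source of error.* The documents give no figures for ranking it against ACS or site. The Arm 1 carrier share has SD √(0.2275/250) = 3.0 points, but even at full adherence the removable component has SD √(0.11375/250) = 2.1 points.
- *That the plan excludes genotype.* The named tests do not use it, but for the logistic model the plan is silent.

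Practical objections also stand, and they shape the fix:

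- At full adherence a logistic model with arm, LOF and their interaction separates completely and has no finite estimate.
- An SE that treats the covariate as fixed would then be √(0.16/250) = 2.53 points against a true 3.31, giving about 87% coverage for a nominal 95% interval.
- Where the rapid assay was inconclusive, the physician had no result, so imputing genotype from the discharge drug is unsound.
- The two arms use different assays.
- The SAP is written in the past tense and says that analyses were done after May 31, 2017, so replacing the primary estimator may come too late.

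**Conclusion.** The point holds as a precision improvement. The crude comparison can stand, but it leaves unused a baseline covariate that the trial already plans to hold in both arms. At 35% carriers, 20% usual-care use and 250 per arm, the variance saving is about 6% to 14% across the partial-adherence cases, with a ceiling of 29%. At the planned 15-point difference, the practical gain is an interval at most 16% narrower. It becomes more useful if the difference is nearer 10 points, or within ACS strata, and subgroup comparison is the plan's stated reason for enlarging the sample from 138 to about 250 per group.

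These sizes rest on assumed adherence, on control use unrelated to genotype, on near-complete genotype calls and, for the subgroup figures, on an even ACS split. They do not support a claim of bias, inflated type I error or inadequate power at the planned effect.

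**What to change.** In SAP item 27a and Protocol 7.1:

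- Report the marginal risk difference between arms standardised to the pooled LOF distribution, with a 95% CI and a two-sided test. Compute it directly from the four arm-by-LOF proportions, so that cells at 0% or 100% cause no separation. This keeps the same marginal quantity, whereas a coefficient from an adjusted logistic model would be a conditional odds ratio.
- Use a variance formula or bootstrap that includes sampling variation in the carrier share.
- Where consent and sample allow, take LOF status from the same saliva array in both arms. This also classifies Arm 1 patients whose rapid test was inconclusive.
- Carry missing genotypes as a separate category, with counts by arm, and do not impute Arm 1 genotype from the discharge drug.
- State which covariates, if any, the planned logistic regression contains.
- Keep the crude chi-square or Fisher result alongside. If outcome data have already been seen, label the standardised estimate as supportive and leave the primary analysis unchanged.

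The cost is a small amount of extra analysis, possible array typing of Arm 1 saliva, and reliance on complete genotype calls. No further patients are needed.

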### 7.2 Secondary endpoints

1. Implementation.
  - a. We will estimate adherence to suggested treatment recommendations based on results of the *CYP2C19* genetic test. The adherence rate is defined as the number of participants in Arm 1 with LOF variants that received prasugrel or ticagrelor + the number of participants without these variants that received clopidogrel divided by the total number in Arm 1.
  - b. We will tabulate reasons for non-adherence to recommendations.
2. Clinical outcomes.
  - a. Frequencies of CV related death, MI, stroke urgent, need for revascularization and stent thrombosis will be reported as will frequencies of bleeding complications. We will determine time to first major cardiac event as a composite endpoint (CV related death, MI, stroke urgent need for revascularization and stent thrombosis). The incidence of first MACE and first major bleeding events between the groups will be compared by use of Kaplan-Meier estimators and statistical tests will be evaluated based on log-rank tests.
  - b. To determine whether MACE outcomes differ in participants with ACS, an interaction term between ACS and group assignment will be tested in a Cox proportional hazard model.
3. Medical service utilization. We will develop descriptive statistics for use of antiplatelet drugs, use of other cardiovascular medications, number of hospitalizations, number of physician visits, and use of rehabilitation services
4. Direct medical cost. We will also develop descriptive statistics for total cost, *CYP2C19* genetic testing cost, medication cost, hospitalization cost, physician visit cost, and rehabilitation cost.
5. Preference scores / QALYs. We will develop descriptive statistics for the SF-12 physical and mental scale scores, the SF-6D, a preference-based health-related quality of life score that can be derived from the SF-12, and for QALYs, a composite measure of its quality (based on the SF-6D). We will also report the correlation between the difference in cost and difference in QALYs (this correlation will be used in sample size estimation for the full study that this pilot study is designed to support).
6. Incremental cost-effectiveness ratio. Based on the differences in primary outcomes total cost and QALYs, we will calculate the ratio incremental costs divided by incremental QALYs, the 95% CI for this ratio, and the cost-effectiveness acceptability curve.

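### SAP item 27f asks whether genotyping influenced MACE in ACS patients, but the ACS-by-arm interaction test it names answers a different question

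*SAP*

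**What the plan says.** SAP Section 6, item 27f, states: "To evaluate whether genotyping influenced MACE outcomes in participants with ACS, an interaction term between ACS and group assignment was tested". The model is a Cox regression, and no other analysis is named for this aim.

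Protocol 7.2, item 2b names the same test with a different aim: "To determine whether MACE outcomes differ in participants with ACS, an interaction term between ACS and group assignment will be tested".

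The other planned MACE comparison between arms uses the arms as a whole: "The incidence of first MACE and first major bleeding events between the groups was compared by use of Kaplan-Meier estimators", with log-rank tests (SAP item 27a; Protocol 7.2, item 2a). The post-hoc Cox models (SAP item 29; Protocol 7.4) group participants by genotype and discharge drug, with history of ACS only as a covariate. Neither document names an arm hazard ratio within ACS or within stable disease.

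Two design features bear on the point. On allocation, the SAP says: "Randomization was stratified by hospital site and by the presence or absence of ACS". On sample size, it says: "We increased our sample size to ~250 per group to allow for subgroup comparisons (e.g. ACS vs. stable coronary disease"). Neither document gives a power figure for MACE, for a subgroup or for the interaction.

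**The concern.** The aim in item 27f is a statement about one stratum: did the genotyping arm have a different MACE hazard from usual care among ACS participants? The interaction coefficient is a statement about two strata: is the hazard ratio in ACS different from the hazard ratio in stable disease? These are different hypotheses, and the plan offers the second as the answer to the first.

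The mismatch can mislead in both directions. A benefit of equal size in ACS and stable disease is an influence in ACS that the test is not built to see. An effect confined to stable disease can make the test significant although nothing happened in ACS. What is at stake is the reading of one secondary subgroup result.

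**Working it through.** **1. The plan's own figure.** The only power statement is for prescribing: "A sample size of 138 per group (a total of 276) would provide 80% power at an alpha level of 0.05", for "35% in the genotyped group and 20% in the control group". With pooled p = 0.275, two-sided alpha 0.05 and no continuity correction:

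n = [1.96·√(2·0.275·0.725) + 0.842·√(0.35·0.65 + 0.20·0.80)]² / 0.15² = 137.9, i.e. 138 per group.

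It reproduces, but it concerns the prescribing endpoint and says nothing about MACE.

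**2. The two hypotheses.** Write the planned model as log h(t) = log h₀(t) + b₁·arm + b₂·ACS + b₃·arm·ACS.

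- log HR in stable disease = b₁; log HR in ACS = b₁ + b₃.
- Test named in 27f: H₀: b₃ = 0, i.e. HR(ACS) = HR(stable).
- Question asked in 27f: H₀: b₁ + b₃ = 0, i.e. HR(ACS) = 1.

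With HR 0.5 in both strata, b₃ = 0 but b₁ + b₃ = ln 0.5. With HR 1.0 in ACS and 0.5 in stable disease, b₁ + b₃ = 0 but b₃ = ln 2. Neither null implies the other. This step needs no assumed numbers.

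**3. Size.** The documents give no MACE rate, ACS share or target hazard ratio, so everything in steps 3 to 5 is assumed. Allocation is 1:1 ("were randomized 1:1 to either rapid genotyping" or usual care), so the variance of a stratum log HR is about 4/events in that stratum. Then SE(b₃) = √(4/e_ACS + 4/e_stable) and SE(b₁ + b₃) = √(4/e_ACS). The rejection rate is Φ(|effect|/SE − 1.96) + Φ(−|effect|/SE − 1.96).

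For 60 events, 30 in each stratum: SE(b₃) = √(4/30 + 4/30) = 0.516 and SE(b₁ + b₃) = √(4/30) = 0.365.

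| True HR, ACS / stable | Interaction test rejects | Direct ACS contrast rejects |
|---|---|---|
| 0.5 / 0.5 | 5.0% | 47.5% |
| 1.0 / 0.5 or 1.0 / 2.0 | 26.9% | 5.0% |
| 0.5 / 1.0 | 26.9% | 47.5% |

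Over 40-100 events with 50-60% in ACS:

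- Row 1: interaction 5.0% throughout; ACS contrast 34-77%.
- Row 2: interaction 19-41%; ACS contrast 5.0% throughout.

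**4. Check by simulated Cox fits.** Assumptions: N = 500, half with ACS, 15% control event rate, 600 runs per scenario.

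| True HR, ACS / stable | Interaction | ACS contrast |
|---|---|---|
| 0.5 / 0.5 | 3.7% | 43.5% |
| 1.0 / 0.5 | 26.2% | 2.8% |
| 1.0 / 2.0 | 33.8% | 4.8% |
| 0.5 / 1.0 | 26.2% | 38.5% |

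The pattern agrees with the approximation.

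**5. Power of both contrasts at lower event counts.** Assume 25-75 events (5-15% of 500) with 50-70% in ACS. The interaction has 12-32% power for HR 0.5 in ACS against 1.0 in stable disease. The direct ACS contrast has 23-71% power for HR 0.5 and 15-46% for HR 0.6.

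**The case against.** The strongest reply is that 27f is loosely worded and not wrongly analysed. The sample size was raised for a comparison of ACS with stable disease, and Protocol 7.2 item 2b asks whether outcomes differ in ACS participants. For effect modification an interaction test is the proper tool. This stands in part: the test is legitimate, and rewording the aim would remove the contradiction. It does not rescue 27f as written, which states a within-ACS aim that its only named analysis cannot meet.

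Second, the 5% figure under equal effects holds for every interaction test, and low power for effect modification is a separate complaint resting on assumed event counts. Both are true. The mismatch is logical and does not depend on them.

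Third, a direct ACS contrast is also underpowered over much of the assumed range, and SAP item 17 makes no multiplicity correction. This stands, and it rules out making the ACS hazard ratio a decisive test.

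Fourth, Protocol 7.0 promises 95% CIs for reported differences. That is partial cover only: it names no within-ACS contrast, and SAP item 18 mentions CIs only for receipt of antiplatelet agents.

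A reader might infer more: that a null interaction is likely whatever the truth, or that the investigators would report it as no effect in ACS. The documents support neither. A large enough difference between strata would be detected, and no rule for interpreting a non-significant result is stated.

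**Conclusion.** The point holds as a mismatch between aim and analysis in SAP item 27f. With equal true effects in both strata, the interaction test rejects at 5% for any number of events. With no effect in ACS and HR 0.5 or 2.0 in stable disease, it rejects 19-41% of the time, given 40-100 assumed events with 50-60% in ACS. Neither outcome of the test tells the reader whether genotyping influenced MACE in ACS, and nothing else in either document estimates that effect.

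The protocol's version is loose but nearer to effect modification, so there the defect is mainly inconsistency with the SAP. MACE is a secondary endpoint, and the sample size rests on prescribing. The primary conclusion and the whole-arm MACE comparison do not change.

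**What to change.** In SAP item 27f and Protocol 7.2 item 2b:

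- State one aligned aim, and describe the interaction test as a test of effect modification by ACS.
- From the planned Cox model, report the arm hazard ratio with 95% CI within stable disease, exp(b₁), and within ACS, exp(b₁ + b₃), using the coefficient covariance for the latter. ACS was a stratification factor, so both are randomized comparisons.
- Report the interaction beside them as a ratio of hazard ratios, exp(b₃), with its CI and p-value, and give the number of events in each stratum.
- State that a non-significant interaction is not evidence of no effect in ACS, and that a significant one does not by itself show an effect there.
- Label the stratum hazard ratios as estimates for a secondary, exploratory subgroup question, without multiplicity control and with limited power.

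The cost is a few sentences and two contrasts from a model already planned. No new data, model or change in sample size is needed.

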### **7.4 Post-hoc analyses**

Genotyped will be determined in the control group at the end of the trial. We will combine the groups and evaluate outcomes by CYP2C19 genotype and antiplatelet drugs prescribed at discharge.

Participants will be grouped into the following categories: 1) Carriers of normal function alleles receiving any antiplatelet drug, 2) LOF carriers receiving clopidogrel, or 3) LOF carriers receiving prasugrel or ticagrelor. Time to MACE, major bleeding and a composite safety/efficacy endpoint consisting of MACE, major bleeding and non-cardiac mortality will be determined in the three groups. Cox proportional hazards models will be used to assess the effects of having an LOF allele and receiving clopidogrel therapy, having an LOF allele and receiving alternative therapy, and not having an LOF allele on the occurrence of first MACE, first major bleed, and first composite outcome. The Cox model will be controlled for age at entry to the study, the date of catheterization, gender, race, hospital site, and history of ACS, smoking, hypertension, diabetes, and myocardial infarction.

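### The post-hoc Cox model for first major bleed carries at least 12 parameters with no method for sparse events: at an assumed 2–5% bleeding rate, infinite hazard ratios are a real risk at the low end and intervals are very wide throughout

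*SAP*

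**What the plan says.** The analysis appears under post-hoc analyses in Protocol 7.4 and as item 29 in Section 6 of the SAP. Both arms are pooled and participants are classed as "1) Carriers of normal function alleles receiving any antiplatelet drug, 2) LOF carriers receiving clopidogrel, or 3) LOF carriers receiving prasugrel or ticagrelor". Cox models then assess these groups "on the occurrence of first MACE, first major bleed, and first composite outcome".

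The adjustment is one fixed list for all three outcomes: "The Cox model was controlled for age at entry to the study, the date of catheterization, gender, race, hospital site, and history of ACS", followed by smoking, hypertension, diabetes and prior MI. SAP item 26a restricts major bleeding to BARC type 3 or 5.

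On size, SAP item 11 says: "We increased our sample size to ~250 per group to allow for subgroup comparisons". It puts the frequency of loss-of-function (LOF) variants at roughly 30–35%.

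Neither document gives an expected bleeding rate or event count, a coding for race in the model, a rule for few events, a penalised or reduced model, or a plan for non-convergence.

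**The concern.** The two groups of interest share only about a third of the participants, and the outcome is limited to the more serious bleeds. Ordinary partial likelihood breaks down when events are few relative to parameters. If a group or covariate level has no events, its coefficient runs off to infinity. Short of that, Wald intervals become unreliable and single events can move the estimate.

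This matters because Protocol 2.0 itself presents bleeding as the cost that accompanies prasugrel's reduction in cardiac events. The post-hoc models are the only planned adjusted analysis relating genotype and drug received to outcome. An unstable bleeding hazard ratio printed beside a steadier MACE hazard ratio could distort that balance in either direction. If the fit failed, the choice of which covariates to drop would be made after seeing the data.

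**Working it through.** **The plan's own figure.** The only power calculation is for prescribing: "35% in the genotyped group and 20% in the control group", for which the stated 138 per group "would provide 80% power at an alpha level of 0.05 to detect this difference". With pooled proportion 0.275 and a two-sided test:

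n = [1.96 × √(2 × 0.275 × 0.725) + 0.8416 × √(0.20 × 0.80 + 0.35 × 0.65)]² / 0.15² = 3.103 / 0.0225 = 137.9, so 138.

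This reproduces. There is no corresponding figure for bleeding to reproduce.

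**Parameters.** Three exposure groups give 2 terms. The covariates are age, catheterization date, gender, race, site, ACS, smoking, hypertension, diabetes and MI, at least 10 terms. The minimum is 2 + 10 = 12. The only race list in the documents (patient survey, Protocol Appendix B) has six categories. Coded in full it would add four more terms, giving 16.

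**Events per parameter.** The bleeding rate is an assumption. At N = 500, events = 500 × rate, divided by 12. Outside the 2–5% range, 1% gives 5 / 12 = 0.42 and 10% gives 50 / 12 = 4.2.

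**No bleed in a LOF group.** Example: 30% carriers, with 70% of genotyped carriers and 20% of usual-care carriers on prasugrel or ticagrelor (the uptake figures are assumed).

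- LOF on prasugrel/ticagrelor: 75 × 0.7 + 75 × 0.2 = 67.5, a share of 0.135.
- LOF on clopidogrel: 150 − 67.5 = 82.5, a share of 0.165.
- With 10 events and no true effect: 0.835¹⁰ + 0.865¹⁰ − 0.70¹⁰ = 0.165 + 0.235 − 0.028 = 0.37.

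Varying carrier frequency over 30–35% and uptake in the genotyped arm over 50–100% gives the ranges in the table.

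**Any infinite estimate, and interval width.** Trials were simulated with N = 500, no true effect, binary race and assumed covariate prevalences, at 300 trials per event count, and checked for at least one infinite coefficient. A separate simulation of 1,500 trials per rate, with 32.5% carriers, gave 54.2%, 25.1% and 6.1% at 2%, 3% and 5%. At 10% every fit was finite.

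| Events (assumed rate) | Events per parameter | A LOF group has no bleed | At least one infinite estimate | Median upper/lower ratio of 95% CI, finite fits |
|---|---|---|---|---|
| 10 (2%) | 0.83 | 29–42% | 54% | 28 |
| 15 (3%) | 1.25 | 12–22% | 25–28% | 21 |
| 20 (4%) | 1.67 | 5–12% | 9% | 13 |
| 25 (5%) | 2.08 | 2–7% | 4–6% | 9 |

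Varying the simulation assumptions moved the infinite-estimate figure to 48–57% at 10 events and 2–6% at 25. A rough unadjusted check on width for the prasugrel/ticagrelor group, exp[3.92 × √(1/(0.135D) + 1/(0.70D))] with D events, gives 39.8 at D = 10 and 10.3 at D = 25, the same order.

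**Race coding.** With six race levels at assumed shares, some coefficient was infinite in 96–100% of runs at 10 to 25 events (100 runs each), mostly a race term.

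**Penalised fit.** In a small simulation (60 trials per rate at 2%, 3% and 5%), the ordinary model had an infinite estimate in about 53%, 28% and 5%, and an infinite exposure effect in about 35%, 15% and 3%. A Firth-penalised Cox model with all 12 parameters was finite in every trial, with profile-likelihood coverage of 97–100%. With so few trials that coverage is only a rough figure.

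**The case against.** The strongest reply has four parts.

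- **The event count is not in the documents.** The synopsis allows 500–600 subjects, and records are reviewed to a fixed date, so some participants may be followed beyond a year. At 600 and 5% there would be 30 events, or 30 / 12 = 2.5 per parameter.
- **An infinite coefficient somewhere is not an infinite exposure effect.** A race term can diverge while the LOF contrasts stay finite. For a single contrast in the example above, the chance of no events at 10 bleeds is 17% or 24%, not 54%.
- **The analysis is labelled post-hoc.** The primary outcome is prescribing. The randomised bleeding comparison uses frequencies, Kaplan-Meier curves and a log-rank test, none of which depend on this model.
- **Penalisation adds no information.** With no bleeds in a group it returns a finite number, but the data remain thin.

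All four stand as limits on the point. A reader might infer from the parameter count that the bleeding hazard ratios will usually be infinite. The documents do not support that: they state no rate, and at 20–25 events with binary race the share of fits with any infinite estimate is only about 4–9%. The reply does not supply a sparse-event method, and the post-hoc label does not excuse its absence, since the model is written out in both documents.

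**Conclusion.** The point holds in limited form. The first-major-bleed model has at least 12 parameters. At N = 500 it has fewer than 5 events per parameter at any rate from 1% to 10%, and no provision is made for sparse events. At an assumed 2–5%, infinite estimates are common near 10–15 events and uncommon near 25. Across that range the typical 95% interval for an exposure hazard ratio spans about 9-fold to 28-fold even when everything is finite. These sizes rest on the assumed bleeding rate, drug uptake, covariate prevalences and no true effect.

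A reader might extend this to the MACE and composite models or to the trial's main results. Neither follows: at an assumed 10% event rate every simulated fit was finite, and the primary outcome and randomised log-rank tests do not use this model. The importance is moderate to low, but the defect is real and cheap to remove.

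**What to change.** In SAP item 29 and Protocol 7.4, for the first-major-bleed model only:

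- keep the listed covariates, but fit by Firth-penalised partial likelihood with profile-likelihood 95% confidence intervals;
- enter race in a collapsed coding fixed in advance;
- report event counts in each of the three exposure groups beside the hazard ratios, and label the result exploratory.

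Leave the MACE and composite models as written. An events-per-parameter trigger is not advisable: a cut-off of 5 would also catch a MACE model with 50 events (50 / 12 = 4.2), where no fit failed. Nor should the main adjustment be cut to age and ACS alone. The treating physician chooses the drug, so the comparison is not randomised. Protocol 2.0 reports allele frequency varying by ancestry, and site is a randomisation stratum (SAP item 10). A reduced model can be shown as a sensitivity analysis.

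The cost is a few lines of wording, a penalised-Cox routine and slight shrinkage of the estimates. As the SAP is written in the past tense, it may also mean refitting this one model.
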